3.2 Trial Treatments

During the double-blind treatment phase, subjects will receive IMP consisting of brexpiprazole monotherapy or placebo, depending on the subject's treatment assignment.

As shown in Table 3.2-1, subjects will receive a starting dose of 2 mg/day of brexpiprazole (or corresponding placebo) from Days 1 to 3, followed by titration to 3 mg/day brexpiprazole (or placebo) on Day 4. Subjects may be titrated (or re-titrated) to a higher dose of brexpiprazole (or placebo), up to a maximum of 4 mg/day, based on treatment response and at the investigator's discretion anytime at Day 7 or thereafter. Subjects who are unable to tolerate their current dose can be titrated down at any time to a minimum of 2 mg/day. Dose adjustments must be made in increments of 1 mg/day. Subjects who are unable to tolerate 2 mg/day brexpiprazole will be discontinued from the trial.

Table 3.2-1 Dosing Schedule			
Dose	Days 1-3	Days 4^a	Days 7-21^b
Brexipiprazole	2 mg	3 mg	2-4 mg
Placebo	Placebo	Placebo	Placebo

^aDown titration can occur at any time due to tolerability after Day 4. The minimum dose allowed is 2 mg/day.

^bOption to titrate 2 to 4 mg (i.e., 2 mg, 3 mg, or 4 mg) based on clinical response and tolerability; changes must occur in 1 mg/day increments. Increases up to 4 mg/day may occur no earlier than Day 7.

All doses of IMP should be taken at the same time each day, if possible, and can be taken without regard to meals. If tolerability issues arise, the timing of administration of the IMP may be adjusted at the investigator's discretion in order to achieve optimum tolerability and compliance. Subjects will be counseled on the importance of taking the IMP.

4 Sample Size and Power Justification

It is anticipated that approximately 320 subjects will be randomized from an estimated 45 sites in the US and Europe. The primary efficacy endpoint is the change from baseline to Day 21 in the double-blind treatment phase in the YMRS Total Score. The trial will compare the placebo arm to the brexpiprazole arm, randomized at a ratio of 1:1, with an overall significance level of 0.05 (2-sided) for the primary endpoint.

CCI

CCI

The planned sample size of 304 evaluable subjects (152 in each treatment arm) will yield at least 90% power to detect the treatment effects at a 2-tailed significance level of 0.05.

A sufficient number of subjects will be enrolled and randomized to achieve approximately 304 evaluable subjects in the double-blind treatment phase CCI

the total number of subjects to be randomized is 320 (160 in each treatment arm).

In order to ensure 304 evaluable subjects, CCI

5 Data Sets for Analysis and Missing Data

5.1 Data Sets for Analysis

The following analysis samples are defined for this trial:

Enrolled Sample: comprises all subjects who signed an ICF for the trial and enrolled into the trial.

Randomized Sample: comprises all subjects who were randomized in the double-blind treatment phase. Subjects are considered randomized when they are assigned a treatment number by IWRS at the end of screening. A subject receiving IMP outside of the IWRS will not be considered randomized, but safety will be reported.

Safety Sample: comprises those randomized subjects in the double-blind treatment phase who received at least 1 dose of double-blind IMP as indicated on the dosing record. Subjects will be excluded from this population only if there is documented evidence (i.e., drug dispensed = drug returned or no IMP dispensed) that the subject did not take IMP. If a subject is dispensed IMP and is lost to follow up, he/she will be considered exposed.

[figure not shown]
Efficacy Sample: The Full Analysis Set comprises all subjects in the Safety Sample who have a baseline value and at least 1 valid post-randomization efficacy evaluation for YMRS Total Score in the double-blind treatment phase.

5.2 Handling of Missing Data

The YMRS is utilized as the primary efficacy assessment of a subject's level of manic symptoms. The YMRS consists of 11 items: 1) elevated mood, 2) increased motor activity-energy, 3) sexual interest, 4) sleep, 5) irritability, 6) speech (rate and amount), 7) language-thought disorder, 8) content, 9) disruptive-aggressive behavior, 10) appearance, and 11) insight. Seven items are rated on a 0- to 4-scale, while four items (Items 5, 6, 8, and 9) are rated on a 0- to 8-scale with 0, 2, 4, 6, and 8 being the possible scores (twice the weight of the other items). For all items, 0 is the "best" rating and the highest score (4 or 8) is the 'worst' rating. The YMRS Total Score is the sum of ratings for all 11 items; therefore, possible total scores range from 0 to 60. The YMRS Total Score is set to be missing if less than 9 of the 11 items are recorded. If 10 of the 11 items are available and the item missing is from items 5, 6, 8 or 9, then the YMRS Total Score is the sum of scores for items 1 to 4, 7, 10 to 11 plus the mean of the recorded items from 5, 6, 8 and 9 times four. If 10 of the 11 items are available and the item missing is from items 1 to 4, 7, 10 to 11, then the YMRS Total Score is the sum of scores for items 5, 6, 8 and 9 plus the mean of the recorded items from 1 to 4, 7, 10 to 11 times seven. If 9 of the 11 items are available and both missing items are from items 5, 6, 8 and 9, then the YMRS Total Score is set to be missing. If 9 of the 11 items are available and both missing items are from items 1 to 4, 7, 10 to 11, then the YMRS Total Score is the sum of scores for items 5, 6, 8 and 9 plus the mean of the recorded items from 1 to 4, 7, 10 to 11 times seven. If 9 of the 11 items are available and one of the missing items is from items 1 to 4, 7, 10 to 11, and one of the missing items is from items 5, 6, 8 and 9, then the YMRS Total Score is the mean of the recorded items from 5, 6, 8 and 9 times four, plus the mean of the recorded items from 1 to 4, 7, 10 to 11 times seven. All imputed scores are rounded to the first decimal place.

CCI

6 Study Conduct

6.1 Subject Disposition, Completion Rate and Reasons for Discontinuation

Subject disposition will be summarized for the Randomized Sample by the treatment group, and by center.

Subject completion rate and reasons for discontinuation will be summarized for the Randomized Sample by treatment group.

6.2 Treatment Compliance

Based on the Investigational medicinal product (IMP) panel of the CRF, compliance in taking IMP is calculated by dividing the number of tablets/capsules taken by the total number of tablets/capsules the patients were scheduled to take during the study period. For lost-to-follow up patients, last IMP end date record will be used as the treatment end date.

6.3 Protocol Deviation

Protocol deviations will be summarized by center and type of deviation for randomized subjects by treatment group. A listing of protocol deviations will be provided.

7 Baseline Characteristics

7.1 Baseline Definition

For analyses of the double-blind treatment period data, the baseline is the Baseline measurement (expected to be at Day 1). Baseline measurement is defined as the last available measurement prior to the start of double-blind IMP.

7.2 Demographic Characteristics

Baseline demographic characteristics include age, sex, race, ethnicity, height, weight, waist circumference, and body mass index (BMI). For the Randomized Sample, demographic characteristics will be summarized by treatment group.

Mean, range and standard deviation will be used to describe continuous variables such as age. Frequency distributions will be tabulated for categorical variables such as race.

7.3 Medical and Psychiatric History

A summary of medical, psychiatric, and bipolar I disorder history will be presented for the Randomized Sample (by treatment group and overall).

7.4 Neuropsychiatric Diagnosis

A summary of the MINI International Neuropsychiatric Interview (M.I.N.I.) will be presented for the Randomized Sample (by treatment group and overall). Summarized will be the number and percentage of patients who meet each diagnosis criteria, and number and percentage of patients with each primary diagnosis.

7.5 Baseline Psychiatric Evaluation

For the Randomized Sample, baseline psychiatric scale evaluation will be summarized by treatment group and overall. The mean, median, range and standard deviation will be used to summarize the assessments of: YMRS Total Score, Clinical Global Impression – Bipolar

(CGI-BP) severity score in mania, **CCI**

8 Efficacy Analysis

All efficacy analyses pertaining to the double-blind treatment period will be performed on the Efficacy Sample, and patients will be included in the treatment group as randomized.

Statistical comparisons are based on 2-sided, 0.05 significance levels.

8.1 Primary Efficacy Endpoint

The primary efficacy endpoint is the change from baseline to Day 21 of the double-blind treatment phase in YMRS Total Score. For analysis of the double-blind treatment phase data, baseline is defined as the last available measurement prior to the first dose of double-blind IMP.

8.1.1 Primary Efficacy Analysis

[figure not shown]
The objective of the primary analysis is to demonstrate the efficacy of brexpiprazole for the acute treatment of manic episodes, with or without mixed features, in subjects with a diagnosis of bipolar I disorder.

The estimand for the primary efficacy analysis is the difference in outcome improvement if all subjects tolerated and adhered to their treatment. This approach is Estimand #3 recommended by the 2010 National Academy of Sciences' National Research Council report on prevention and treatment of missing data and ICH E9 (R1) "Addendum to Statistical Principles for Clinical Trials on Choosing Appropriate Estimands and Defining Sensitivity Analyses in Clinical Trials".

[figure not shown]
This estimand focuses on the efficacy of brexpiprazole in change from the baseline in YMRS Total Score. The objective of this trial is consistent with the election of an efficacy rather than effectiveness estimand.

The primary analysis will be performed on the Efficacy Sample which includes all randomized subjects who took at least 1 dose of IMP in the double-blind treatment phase and who have both a baseline value and at least 1 post-randomization YMRS Total Score during the double-blind treatment phase. The primary efficacy analysis will be performed by fitting a mixed-effect model repeated measure (MMRM) analysis with an unstructured variance covariance structure in which the change from the baseline in YMRS Total Score during the

double-blind treatment phase will be the dependent variable based on the observed cases (OC) data set. The OC data set will consist of actual observations recorded at each visit during the double-blind treatment phase and no missing data will be imputed. **CCI**

CCI

8.1.3.2

CCI

**8.1.4 Subgroup Analyses**

Subgroup analyses of change from baseline in YMRS Total Score to every study week in the double-blind treatment period will be performed by the following factors:

- Sex (Based on the biological status)
- Race (White and All Other Races)
- Age group (Age<55 and Age≥55)
- Region (North America and Europe)

All subgroup analyses will be conducted using the same MMRM analysis as for the primary efficacy analysis except that the fixed class effect term for trial center will not be included in the model

9.1 Adverse Events

All adverse events will be coded by System Organ Class (SOC) and Preferred Term (PT) according to the Medical Dictionary for Regulatory Activities (MedDRA). AEs that are sex-specific, e.g., ovarian cancer, will have their incidence rates evaluated for the specific sex.

Treatment-emergent AEs (TEAEs) are defined as AEs with an onset date on or after the start of double-blind treatment period. In more detail, TEAEs are all adverse events which started after start of double blind IMP; or if the event was continuous from baseline and was worsening, serious, study drug related, or resulted in death, discontinuation, interruption or reduction of study therapy. Adverse events occurring up to 30 days after the last day of IMP will be included in the summary tables.

The incidence of the following events in the double-blind treatment period will be tabulated by treatment group and overall using the Safety Sample:

- a) TEAEs
- b) TEAEs by severity
- c) TEAEs potentially causally related to the IMP
- d) TEAEs with an outcome of death
- e) Serious TEAEs
- f) TEAEs leading to discontinuations of the IMP

The above summaries (b), (e) and (f) will also be prepared for TEAEs potentially causally related to the IMP.

In addition, incidence of TEAE during the double-blind treatment period of at least 5% in any treatment group other than placebo group, and also greater than placebo by SOC and PT will be provided.

Incidence of TEAEs by SOC and PT will be summarized for sex, race, age and region subgroups.

CCI

Unless otherwise specified, in general, analysis of safety data will be performed on observed case and for last visit.

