	
C
      
Safety Endpoints:
 
Standard safety variables will include AEs, clinically significant changes in: ECGs, vital signs, clinical laboratory tests, use of concomitant medications, changes in body weight, and PE.
 
CCI
  
Suicidality will be assessed using the C-SSRS.

Statistical Methods:
	
For analysis of the double-blind treatment phase data, baseline is defined as the last available measurement prior to the first dose of double-blind IMP. The primary analysis will be performed on the Efficacy Sample which includes all

randomized subjects who took at least 1 dose of IMP in the double-blind treatment phase and who have both a baseline value and at least 1 post-randomization YMRS Total Score during the double blind treatment phase. CCI

[REDACTED]

[REDACTED]

[REDACTED]

The primary efficacy endpoint is the change from baseline to Day 21 in the double-blind treatment phase in the YMRS Total Score. The trial will compare the placebo arm to the brexpiprazole arm, randomized at a ratio of 1:1, with an overall significance level of 0.05 for the primary endpoint.

CCI [REDACTED]

The planned sample size of 304 evaluable subjects (152 in each treatment arm) will yield at least 90% power to detect the treatment effects at a 2-tailed significance level of 0.05.

A sufficient number of subjects will be enrolled and randomized to achieve approximately 304 evaluable subjects in the double-blind treatment phase CCI

[REDACTED]

the total number of subjects to be randomized is 320 (160 in each treatment arm).

	
In order to ensure 304 evaluable subjects, ^{CCI} [REDACTED]

Trial Duration:
	
The duration of this trial for an individual subject who completes the trial without early withdrawal is approximately 8 weeks. This is inclusive of a maximum 14-day screening period, a 3-week double-blind treatment period, and a safety follow-up via telephone contact or clinic visit 21 (\pm 2) days after the last dose of IMP. Subjects who complete all trial visits through the Day 21 visit may be offered entry into an optional open-label rollover trial.

Table of Contents

Protocol Synopsis	2
Table of Contents	7
List of In-text Tables	12
List of In-text Figures	13
List of Appendices	14
List of Abbreviations and Definitions of Terms	15
1 Introduction	17
1.1 Nonclinical Data	17
1.2 Clinical Data	18
1.3 Known and Potential Risks and Benefits	18
2 Trial Rationale and Objectives	19

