5.2 Eliciting and Reporting Adverse Events

The investigator will periodically assess subjects for the occurrence of AEs. To avoid bias in eliciting AEs, subjects should be asked the non-leading question: "How have you felt since your last visit?" All AEs (serious and nonserious) reported by the subject must be recorded within the eSource platform provided by the sponsor. All AE collection is to begin after a subject has signed the ICF.

Use medical terminology in AE reporting. Adverse events should be reported as a single unifying diagnosis whenever possible or, in the absence of a unifying diagnosis, as individual signs or symptoms. Exacerbation or disease progression should be reported as an AE only if there are unusual or severe clinical features that were not present, or experienced earlier, or not expected based on the course of the condition.

A reported AE that undergoes a change in severity, seriousness, or toxicity should be reported as a new AE on the ePlatform.

In addition, the sponsor must be notified immediately by telephone, fax, or e-mail of any IREs according to the procedure outlined below, in [Section 5.3](#). Special attention should be paid to recording hospitalization and concomitant medications.

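### SAP 9.1 defines treatment-emergent AEs twice, and the second definition lets in an unchanged pre-dose event because it is serious (minor)

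*SAP*

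**What the plan says.** SAP 9.1 opens its definition with an onset rule: "Treatment-emergent AEs (TEAEs) are defined as AEs with an onset date on or after the start of double-blind treatment period". The next sentence restates it: "In more detail, TEAEs are all adverse events which started after start of double blind IMP". It then adds a second route: "or if the event was continuous from baseline and was worsening, serious, study drug related". The list ends with events that had a fatal outcome or that caused dosing to be stopped, paused or lowered.

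The tables built on this flag include all TEAEs, TEAEs related to IMP and "e) Serious TEAEs". The severity, serious and discontinuation tables are repeated for related TEAEs.

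Events with pre-dose onset will be in the database. Protocol 5.2 states: "All AE collection is to begin after a subject has signed the ICF". The Protocol Synopsis, on trial duration, says: "This is inclusive of a maximum 14-day screening period". Protocol 7.6.1 lists TEAE tables without defining the term, and Protocol 7.6 leaves the details of the safety analysis to the SAP. Nothing visible elsewhere settles which sentence of SAP 9.1 governs.

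**The concern.** The two sentences classify some events differently. Under the first, an AE that began in screening is never treatment-emergent on that record. Under the second, it is if any one item in the list applies. Most of those items imply that something happened on treatment: the event worsened, someone died, or dosing was stopped, interrupted or reduced. *Serious* and *study drug related* do not. They can describe an event that looked exactly the same the day before the first dose.

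Safety and tolerability is the trial's secondary objective, and the serious-TEAE table is one of the main displays for it. Two programmers working from SAP 9.1 could produce different tables from the same data. Under the wider reading the serious-TEAE table could hold events that no study drug could have started.

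Usage in the protocol does not help. Protocol 4.1.1 applies the term TEAE to anxiety, agitation and insomnia during washout, before any IMP is given.

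**Working it through.** The plan states no figure on this point, so there is nothing to reproduce. The check is to run each kind of event through both sentences.

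| Event | Sentence 1 | Sentence 2 |
|---|---|---|
| Onset on a day after the first-dose day | TEAE | TEAE |
| Onset on Day 1, after the first dose | TEAE | TEAE by clock time; not if only dates are compared |
| Pre-dose onset, ongoing, unchanged, not serious, not related, no consequence for dosing | No | No |
| Pre-dose onset, worsened or became serious after first dose | Old record no; new record yes | TEAE |
| Pre-dose onset, unchanged, led to a dosing change | No | TEAE |
| Pre-dose onset, already serious, unchanged | No | TEAE and serious TEAE |
| Pre-dose onset, unchanged, judged related | No | TEAE and related TEAE |

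**The new-record rule.** Protocol 5.2 has a change in severity or seriousness reported as a new AE. An event that turns serious after dosing therefore gets its own record and can qualify by its own onset. So what the free-standing word *serious* mainly adds is events that were already serious before dosing.

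**The related item.** Protocol 5.1 defines Related as a reasonable possibility of both a time link and a causal link with IMP. An event that preceded IMP and did not change would not normally be judged so. The last row is possible on the wording but should be nearly empty.

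**Size of one event.** SAP section 4 plans 160 subjects per arm, so one subject moves an arm's rate by 1/160 = 0.625 percentage points. Suppose true serious TEAEs run at 1% to 3% (an assumption; the documents give no rate). That is 1.6 to 4.8 subjects, or about 2 to 5 per arm, and one more subject adds 1/5 to 1/2, that is 20% to 50%, to the count.

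**Effect on the comparison.** Let p be the true serious-TEAE risk and c the share of subjects bringing in an unchanged serious event. Take c equal in both arms by randomization and independent of p. Then the observed risk = 1 − (1 − p)(1 − c). For example, with p = 4% and c = 1%: 1 − 0.96 × 0.99 = 0.0496, or 160 × 0.0496 = 7.94 subjects. All p and c below are assumptions.

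| p, placebo / brexpiprazole | c | Expected subjects per arm of 160, placebo / brexpiprazole | Risk ratio | Risk difference (points) |
|---|---|---|---|---|
| 2% / 4% | 0 | 3.20 / 6.40 | 2.00 | 2.00 |
| 2% / 4% | 0.5% | 3.98 / 7.17 | 1.80 | 1.99 |
| 2% / 4% | 1% | 4.77 / 7.94 | 1.66 | 1.98 |
| 2% / 4% | 2% | 6.34 / 9.47 | 1.49 | 1.96 |
| 1% / 3% | 0 | 1.60 / 4.80 | 3.00 | 2.00 |
| 1% / 3% | 0.5% | 2.39 / 5.58 | 2.33 | 1.99 |
| 1% / 3% | 1% | 3.18 / 6.35 | 1.99 | 1.98 |
| 1% / 3% | 2% | 4.77 / 7.90 | 1.66 | 1.96 |

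Incidence rises in both arms, the risk ratio moves towards 1, and the risk difference hardly changes.

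**The case against.** The strongest reply is that the subject who triggers the problem is rare. The AE must be serious already, ongoing at first dose and unchanged afterwards, in someone who was still randomized. Eligibility is re-checked at baseline (Protocol 3.7.1.2), clinically significant current disorders are excluded, and the investigator, sponsor or medical monitor may exclude anyone (criteria 16 and 32). The obvious candidate, admission for the manic episode, is largely ruled out: hospitalization is part of the design, Protocol 5.1 says hospitalization itself should not be reported as an SAE, and Protocol 5.2 makes exacerbation an AE only when its features are unusual or severe. This stands, and it limits the size of the effect.

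A second reply is that the author may have meant *became serious*. The SAP does not say so, and given the new-record rule in Protocol 5.2 that reading would add little. The same rule means that the worsening and became-serious conditions in the fix mostly repeat what a new record already captures. That is true but harmless: they cover the case where no new record was made.

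A reader might infer more from the text than it supports:

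- **Pre-treatment events will appear in the tables.** They do so only if the second sentence is the one programmed. Its opening words suggest that it governs, but the first sentence excludes these events.
- **The drug-related tables are contaminated.** The definition of Related in Protocol 5.1 largely prevents it.
- **First-dose-day events are lost.** That requires comparing calendar dates under the second sentence and ignoring the first, which covers "AEs with an onset date on or after the start of double-blind treatment period". Read as clock time, an event later on Day 1 did start after IMP. What remains is a small mismatch of wording.

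**Conclusion.** The inconsistency is real and rests on the text alone. For an unchanged, already serious pre-dose AE, the two sentences of SAP 9.1 give opposite answers, and the wider one has no basis in anything that happened after dosing. It is a minor point. The carried-in events should be few and balanced by randomization, so the expected result is slightly higher incidence in both arms.

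It would be tempting to call this a bias for or against brexpiprazole. The documents do not support that: with equal carry-in the risk difference stays near 2.0 points in every scenario above. The weaker risk ratios depend entirely on the assumed rates, and a carry-in of 1% to 2% is probably generous. The visible text of SAP 9.1 plans incidence tables without hypothesis tests, and the primary and key secondary analyses are unaffected.

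**What to change.** Replace both sentences in SAP 9.1 with one rule. A TEAE is an AE with onset on or after the first dose of double-blind IMP, or an AE present before the first dose that after it worsened in severity, became serious, or led to death or to discontinuation, interruption or reduction of IMP. Remove the free-standing conditions for serious and for drug-related events. List unchanged pre-dose AEs separately as pre-treatment events, so that nothing disappears from reporting. Using *on or after* throughout also removes the Day 1 mismatch.

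The cost is SAP wording and one flag in the AE dataset. No new data are needed.

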3.7 Trial Procedures

This trial is a phase 3, double-blind, placebo-controlled trial to investigate the efficacy, safety, and tolerability of brexpiprazole (2-4 mg/day) for the treatment of subjects with bipolar I disorder experiencing a manic episode with or without mixed features. The trial comprises a 3-week, double-blind treatment period with a 21 (\pm 2) day follow-up.

Trial assessment time points are summarized in Table 3.7-1.

Table 3.7-1 Schedule of Assessments							
	Screening ^a	Double-blind Treatment Phase					Follow-up ^c
	Day -14 to -1	Baseline (Day 1)	Day 4 (± 1 day)	Day 7 (± 1 day)	Day 14 (± 1 day)	Day 21/ET ^b (± 2 day)	21 (± 2) days after last dose
Screening Assessments and Randomization							
Informed Consent ^d	X						
Demographics	X						
Medical History	X						
Psychiatric History	X						
MINI	X						
Concomitant Medications ^e	X	X	X	X	X	X	X
Inclusion/Exclusion Criteria	X	X					
Randomization		X					
Efficacy Assessments							
YMRS ^f	X	X	X	X	X	X	
CGI-BP ^g		X	X	X	X	X	
CCI	█	█			█	█	
		█				█	
Safety Assessments							
Physical Examination ^h	X					X	
Vital Signs ⁱ	X	X	X	X	X	X	
Body Weight	X					X	
12-lead ECG ^j	X	X				X	
Clinical laboratory tests (hematology, serum chemistry, urinalysis), including prolactin ^k	X					X	
HbA1c ^j	X					X	

Table 3.7-1 Schedule of Assessments							
	Screening ^a	Double-blind Treatment Phase					Follow-up ^c
	Day -14 to -1	Baseline (Day 1)	Day 4 (± 1 day)	Day 7 (± 1 day)	Day 14 (± 1 day)	Day 21/ET ^b (± 2 day)	21 (± 2) days after last dose
TSH, with reflex to T ₄ if TSH is abnormal	X					X	
Coagulation parameters (PT, aPTT, INR) ^k	X					X	
Lithium, Valproate, Carbamazepine Levels ^l	X						
HIV, HBsAg, and anti-HCV	X						
Pregnancy Test ^m	X		X			X	
Drug Screen ⁿ	X					X	
Blood Alcohol Test ^o	X					X	
C-SSRS ^p	X	X	X	X	X	X	
CCI							
AEs ^q	X	X	X	X	X	X	X
CCI							
Other							
IMP dispensing ^s		X	X	X	X		
IMP accountability			X	X	X	X	

aPTT = activated partial thromboplastin time; HBsAg = Hepatitis B surface antigen; Anti-HCV = Antibodies to hepatitis C virus; INR = International Normalized Ratio; T₄ = free thyroxine; TSH = thyroid-stimulating hormone.

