3.10 Definition of Completed Subjects

The treatment period is defined as the time period during which subjects are evaluated for primary and/or secondary objectives of the trial irrespective of whether or not the subject actually consumed all doses of the IMP. Subjects who are evaluated at the last scheduled visit during the treatment period will be defined as trial completers. For purposes of this trial, subjects who complete Day 21 visit will be defined as trial completers.

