5.7 Follow-up of Adverse Events

For this trial, information on AEs will be followed for up to 21 (+2) days after the last dose of IMP has been administered.

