5.7.2 Follow-up of Serious Adverse Events

This trial requires that subjects be actively monitored for SAEs up to 21 (+2) days after the last dose of IMP is administered.

Serious AEs that are **identified or ongoing at the last scheduled contact** must be recorded on the AE ePlatform and reported to the sponsor according to the reporting procedures outlined in [Section 5.3](#). This may include **unresolved previously reported SAEs, or new SAEs**. The investigator will follow SAEs until the events are resolved, stabilized, or the subject is lost to follow-up. Resolution means that the subject has returned to the baseline state of health and stabilized means that the investigator does not expect any further improvement or worsening of the subject's condition. The investigator will continue to report any significant follow-up information to the sponsor up to the point the event has been resolved, stabilized, or the subject is lost to follow-up.

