9.8 Concomitant Medications

Number and proportion of patients taking concomitant medications prior to study therapy, during the double-blind treatment period, and after study therapy are tabulated by drug classification using the WHO drug dictionary.

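### SAP 9.1 counts adverse events up to 30 days after the last dose in tables labelled double-blind incidence, mixing on-drug and follow-up events with no visible cut-off at the first open-label dose

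*SAP*

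**What the plan says.** SAP 9.1 defines treatment-emergent events by a start date and gives no end date. It then adds a counting rule: "Adverse events occurring up to 30 days after the last day of IMP will be included in the summary tables". The next sentence introduces tables (a) to (f): "The incidence of the following events in the double-blind treatment period will be tabulated by treatment group and overall using the Safety Sample". The table of common events carries the same label, covering "TEAE during the double-blind treatment period of at least 5% in any treatment group other than placebo group, and also greater than placebo".

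Elsewhere the documents keep treatment and follow-up apart:

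- Protocol 3.7 names the two periods, where the closing number is the length of follow-up in days (± 2): "The trial comprises a 3-week, double-blind treatment period with a 21".
- Protocol 3.10 places the Day 21 visit at the end of the treatment period, in its rule for completers: "the last scheduled visit during the treatment period will be defined as trial completers. For purposes of this trial, subjects who complete Day 21".
- SAP 9.8 tabulates concomitant medication in three periods: "prior to study therapy, during the double-blind treatment period, and after study therapy are tabulated by drug classification".

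On who is followed after the last dose, the protocol is not uniform. Section 3.1 (Follow-up Phase), footnote c of Table 3.7-1 and SAP 3.1 limit the safety contact to subjects who do not enter the open-label trial, early withdrawals included. Protocol 3.7.1.8 does not repeat the rollover exception. Nor does 5.7 ("information on AEs will be followed for up to 21 (+2) days after the last dose of IMP has been administered") or 5.7.2 ("This trial requires that subjects be actively monitored for SAEs up to 21 (+2) days after the last dose of IMP is administered").

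**The concern.** Safety and tolerability is the secondary objective, and these incidence tables are a main visible output for it. A reader of a table headed double-blind incidence will take the events as having arisen on randomized treatment. Under the counting rule some will have arisen after it stopped. After an early stop, new medication may begin once the early-termination assessments are done, so some of these events can arise on another treatment.

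Rollover is also decided after randomization. Protocol 3.1 ties it to completing all visits with no major protocol violation, and it may differ by arm. If only non-rollover subjects are contacted, the chance of recording a follow-up event depends on that outcome. If rollover subjects are followed as well, their events within 30 days can fall after the first open-label dose and still be counted under the arm to which they were randomized.

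**Working it through.** **1. The plan's own duration.** The Synopsis gives about 8 weeks per subject: at most 14 days of screening, 21 of treatment and 21 (± 2) of follow-up. 14 + 21 + 21 = 56 days = 8.0 weeks, which agrees. A 30-day follow-up would give 14 + 21 + 30 = 65 days = 9.3 weeks. No contact is planned at 30 days; the SAP limit runs 30 − 23 = 7 to 30 − 19 = 11 days past the planned contact.

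**2. Observed days per subject, if only non-rollover subjects are contacted.**

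| Subject | On drug | After last dose | Share after last dose |
|---|---|---|---|
| Rollover completer | 21 | about 0 | about 0% |
| Non-rollover completer | 21 | 19 to 23 | 19/40 = 47.5% to 23/44 = 52.3% |
| Stops at Day 7 | 7 | 19 to 23 | 19/26 = 73.1% to 23/30 = 76.7% |

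These shares show how much observation is mixed. They do not measure bias, because the planned tables count subjects with an event and not person-days.

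**3. Illustration A (all inputs assumed).** On-drug incidence p = 4% in both arms; a fraction r of non-rollover subjects has a first onset after the last dose; s is the non-rollover share. Tabulated incidence = p + (1 − p) × r × s.

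| Non-rollover share | r = 2% | r = 5% |
|---|---|---|
| 42.5% in both arms | 4.82% in both; difference 0 | 6.04% in both; difference 0 |
| 35% in one arm | 4.67% | 5.68% |
| 50% in the other | 4.96% | 6.40% |
| Difference, 35% vs 50% | 0.29 points | 0.72 points |

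Per 160 subjects the differences are 0.46 and 1.15 subjects.

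**4. Illustration B (harsher, also assumed).** The daily hazard is the same in both arms, on and off drug. Rollover subjects are observed for 21 days and the others for 42. With on-drug incidence p, the 42-day incidence is 1 − (1 − p)². Rollover is 70% in one arm and 50% in the other.

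- p = 5%: 42-day incidence 9.75%; tabulated 6.43% vs 7.38%, difference 1.0 point (0.95 before rounding).
- p = 10%: 42-day incidence 19%; 0.7 × 10 + 0.3 × 19 = 12.7% vs 0.5 × 10 + 0.5 × 19 = 14.5%, difference 1.8 points.
- p = 20%: 42-day incidence 36%; 24.8% vs 28.0%, difference 3.2 points.

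With 50% rollover in both arms the difference is 0 and only the level rises (10% becomes 14.5%).

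**5. The 5% table.** This table applies a threshold, so a small shift can change what is listed. In A with r = 5%, if brexpiprazole had the higher non-rollover share, a term at 4% on drug in both arms would appear as 6.40% against 5.68% and be listed. With r = 2% (4.96% against 4.67%) it would not.

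**6. The other branch.** If rollover subjects are followed, observation is more even, but the visible rule does not stop at the first open-label dose. The documents do not describe safety recording in the rollover trial, so this branch cannot be sized.

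**The case against.** Counting events for a period after the last dose is a normal convention, and the SAP states its rule openly. Protocol 7.6.1 asks for treatment-emergent incidence by arm and sets no end date, so the SAP does not depart from it. SAP 9.8 is no rule for adverse events. The tables are descriptive, and onset dates allow events to be split later. Table (f), events leading to discontinuation, can hardly contain onsets after the last dose. Ending the tables at the last dose is not neutral either, because early stoppers are then observed for less time. All of this stands. It limits the weight of the point, but the label still does not match the content.

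A reader might infer that rollover subjects certainly have no adverse-event observation after the last dose. The documents do not establish that: footnote c limits a contact, and Protocol 3.7.1.8, 5.7 and 5.7.2 state follow-up without the exception. This leaves the two branches in the working, and neither gives a clean double-blind table.

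A reader might also infer that the SAP omits an on-treatment table or an open-label cut-off. Part of SAP 9.1 is redacted and the list of summary tables in Section 13 is not visible. Either could be there, so only the visible text can be criticized.

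**Conclusion.** The point holds as a matter of definition and labelling. In the visible text, tables called double-blind incidence include follow-up events. Those events are either ascertained unequally by rollover status or, if all subjects are followed, not cut off at the first open-label dose.

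Two stronger conclusions are not supported. The first is that the safety comparison is biased. The documents give no rollover shares or post-dose event rates, so size and direction are unknown. The between-arm effect is nil when both are equal and probably small otherwise. The 0.29 to 0.72 points rest on assumed shares of 35% and 50%. The 1.0 to 3.2 points need both a 20-point rollover gap and an equal hazard on and off drug. The second is that the gap between 30 days and 21 (+2) days is itself the fault. The 30 days limits what is counted and schedules no collection, so among subjects contacted as planned it adds or loses almost no events.

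This is a cheap improvement worth making. The trial's efficacy conclusions do not depend on it.

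**What to change.** In SAP 9.1:

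- For the treatment-emergent tables and the 5% table, count events with onset from the first to the last double-blind dose, plus any lag the sponsor justifies, and never past the first open-label dose.
- Keep the combined table, labelled as including post-treatment follow-up.
- Show post-treatment events descriptively by arm, with the number of subjects actually followed. Note that these subjects are a subset formed after randomization and that the table is not meant for comparison between arms.

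If the redacted sections already contain such tables, only the labels and the date rule need attention. The cost is SAP wording, a date rule and one more table, with no new data. The downsides are that on-treatment tables give early stoppers shorter observation and that late-onset events must be read from the second table.
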